injected. If both eyes have the same acuity the eye with longest onset will be injected. If one eye has <12 months and >6month since onset and the difference in acuity between the eyes is ≤ 10 letters, the eye with ≥ 12 months will be injected. If eyes have an acuity difference >10 letters, the eye with worse acuity will be injected.

Aim 2. To Evaluate the Safety of AAV-ND4 in subjects with acute (<12 months) bilateral loss of visual acuity to ≤ 35 ETDRS letters (Snellen = 20/200) (Group 2). The eye with worse acuity will be injected.

Aim 3. To Evaluate the Safety of AAV-ND4 in subjects with unilateral loss of acuity to ≤ 35 ETDRS letters, but who have “good acuity” ≥ 70 letters (20/40 Snellen) in the contralateral eye (Group 3). The eye with better acuity will be selected for injection.

For each group, administration of study drug will follow an adaptive plan to identify the maximum tolerated dose. If none of the three subjects at a given dose level develops a major toxicity, the next cohort will receive the next higher dose. We will wait a minimum of 6 weeks between injections of the same dose in successive subjects, and will wait until 3 months after the last subject is injected with this dose before moving to the cohort receiving the next higher dose. We will test the lowest dose first in 3 subjects of Aim 1, before moving on to testing this low dose in Aim 2, then lastly in Aim 3. Safety will be monitored for loss of 15 letters in Aims 1 and 2, but a difference of 15 letters worse in the treated eyes relative to untreated eyes for Aim 3. If acuity, and visual field testing demonstrate no toxicity in Aims 1 and 2, we will proceed with Aim 3.

The **objective** of this proposed clinical trial is to evaluate the safety of mitochondrially targeted ND4 gene therapy with the adenoassociated viral vector in appropriate LHON patients in a Phase I clinical trial. If warranted by the results of the Phase I trial, another aim will be to obtain a preliminary estimate of the therapy’s efficacy. We provide a summary of the extensive preclinical testing in relevant rodent animal models to support the efficacy of the approach proposed in this clinical trial.

The **primary hypothesis** being tested is there will be no systemic toxicity or loss of vision to No Light Perception in the injected eye.

4) **Background***

Background and Significance

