Leber’s Hereditary Optic Neuropathy (LHON) is a maternally inherited form of bilateral optic neuropathy causing severe and permanent visual loss in young adults, usually between the second and fourth decades of life. LHON

usually presents as a loss of central vision that typically progresses over weeks without pain, until bilateral central scotomas and visual loss remain. Visual loss may occur in both eyes simultaneously, or in one eye with the fellow eye affected weeks to months later. The deterioration of vision may progress over several months to a maximum loss of function which stabilizes at visual acuities worse than 20/200.

Characterization of the hereditary nature of LHON led early researchers to postulate that it was a disorder of mitochondrial inheritance. Molecular analysis has confirmed that the basic etiology results from a point mutation in mitochondrial DNA (mtDNA). Three primary mutations at nucleotide pair 3460, 11778, and 14484 are generally agreed to be the primary causes of LHON, accounting for 98% of LHON cases. All primary LHON mutations alter mtDNA-encoded protein subunits, which comprise NADH-ubiquinone oxidoreductase (complex I) of the mitochondrial respiratory chain. Therefore, it is generally hypothesized that a dysfunctional respiratory chain impairs ganglion cell function leading to ganglion cell layer and optic nerve damage resulting in vision loss. While the relationship between genotype and phenotype appears straightforward, the selective clinical presentation observed in LHON patients indicates a complex pathogenesis. Although a primary LHON mutation is necessary for the expression of the disease, it is unclear how the mutations interact with other genetic and/or epigenetic factors to cause tissue specific disease in only select individuals.

To date an effective treatment for LHON has not been identified. Anecdotal reports of treatment efficacy have been difficult to interpret given the potential for spontaneous recovery in certain genotypes. Treatments including systemic steroids, hydroxycobalamin, cyanide antagonists, and naturally occurring cofactors (e.g., coenzyme Q10, succinate and idebenone) have not produced definitive evidence of treatment or prevention of visual loss.

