**Escalation from high dose group I to higher dose group II was previously approved. Since chronic bilateral group I individuals are considered at lower risk than group II, there are no additional safety concerns to injecting group I intermixed with group III individuals, after the 3rd group II injection and 3 month safety period. In this combined cohort, each of the 6 injections will be spaced at least 6 weeks apart. Ordering of participants will be determined by their presentation to the study and PI discretion, with the aim of ensuring injection of the more difficult to recruit group III individuals.

7) **Study-Wide Recruitment Methods* N/A for Multi-center trial**

Number of Study Centers: One (1), Bascom Palmer Eye Institute, University of Miami, Miami, FL.

Phase I. A review of the LHON patients currently being seen by [REDACTED] and [REDACTED] with long-standing severe vision loss of 20/200 or worse, shows that we have 23 patients who would be eligible for the Phase 1 study in Groups 1 and 2. We expect that the availability of a potential treatment will draw more patients in groups 2 and 3. Thus, we should have a sizable pool of patients for the Phase 1 safety study of the AAV-ND4 vector.

Individuals who have been diagnosed with G11778A mutation associated Leber's hereditary Optic Neuropathy and who are eligible based on inclusion and exclusion criteria will be invited to participate in this clinical trial. A complete physical examination and clinical chemistries will be performed at a pre-treatment, screening evaluation to further determine eligibility. Subjects will be considered enrolled when they sign the Informed Consent.

Enrollment Procedures:

Eligibility will be assessed at a study team meeting prior to the baseline 2 exam. This meeting must include at least one MD coinvestigator in addition to the PI. Other participants may include clinical staff, biostatistics center staff, and the CRORS office. Minutes will be recorded during these meetings and a sign in sheet will be kept. If the injecting retina specialist is unable to attend the assessment meeting, they will be asked to review and sign off on the eligibility criteria checklist prior to the injection. If the patient meets all inclusion and exclusion criteria a request will be forwarded to the research pharmacist for Study Drug dilution.

8) **Study Timelines***

- The duration of an individual subject's participation in the study:10 years

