Retinal detachment	Localized and intervention not indicated	Not resolving but intervention not yet indicated	Operative intervention indicated	Operative failure threatening ocular integrity*

*

For group III, due to the natural history of LHON where visual loss is expected in the asymptomatic eye, a vision-related SAE will be considered a decrease in acuity in the injected eye to 0.3 logMAR units (15-letter equivalent) worse than the worst acuity measured in the uninjected fellow eye at the current or any prior study visit.

Table 6-7: Systemic toxicity scale

Grade	Definition
1	Mild toxicity, usually transient, requiring no special treatment and generally not interfering with usual daily activities.
2	Moderate toxicity which may be ameliorated by simple therapeutic maneuvers, and impairs usual activities.
3	Severe toxicity which requires therapeutic intervention and interrupts usual activities. Hospitalization may or may not be required.
4	Life-threatening toxicity which requires hospitalization.

Evaluation of Secondary Endpoint – Visual Function Changes

Visual function will be quantified prior to and after vector administration in order to determine whether vector administration affects visual

function. The main measure of visual function will include best corrected ETDRS visual acuity.

10) Procedures Involved*

Method of Assigning Subjects to Treatment Groups:

Subjects enrolled in the study will be assigned to disease groups based on disease manifestation and screening evaluation. All subjects in the study will receive active treatment (one injection of scAAV2-P1ND4v2) at the Low, Medium or High dose as explained in section 6, Number of Subjects.

Study Visits:

Table 6-4 outlines the schedule of planned study evaluations. Subjects will be enrolled and undergo baseline assessments prior to Day 0. Study agent administration which will occur on Day 0 and details of the procedure are included below.

Table 6-4 Study Visit Summary Procedures

Time point	Baseline		Day								Year				
	B1	B2	0	1	7	3	6	9	1	2	3	1.5	2	3	4-10
Informed consent/assent	■														
Blood test for G11778A mutation	■														
History and physical exam	■			■		■		■			■				
Electrocardiogram, chest X-ray		■													
Pregnancy test	■	■													
Vital signs monitoring	■	■	■	■											
Hematology, chemistry, urinalysis	■		■	■	■	■	■	■	■	■	■	■	■	■	■
Coagulation Panel		■													
AAV antibody and specific reactivity (ASR) measurement	■			■				■			■				

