Peripheral blood PCR	■ ⁺			■ ⁺	■ ⁺										
Visual Acuity	■	■	■	■	■	■	■	■	■	■	■	■	■	■	■
Perimetry	■	■	■	■	■	■	■	■	■	■	■	■	■	■	■
PERG	■	■	■	■	■	■	■	■	■	■	■	■	■	■	■
Neuro-ophthalmic Exam	■	■	■	■	■	■	■	■	■	■	■	■	■	■	■
OCT Imaging	■	■		■		■		■		■		■		■	

Fundus photography	■	■	■	■	■	■	■	■	■	■	■	■
Quality of life questions (NEI VFQ-25)	■				■	■	■	■	■	■	■	■
Adverse event recording	■	■	■	■	■	■	■	■	■	■	■	■
Long-term follow-up										■	■	■

Baseline visits are no more than 1 month before day 0, date of vector administration;

⁺testing will continue until two consecutive samples test negative

Detailed Study Procedures

Informed Consent

The use of the informed consent process will ensure that subjects are adequately informed about the study procedures and associated risks and benefits. An investigator will also provide complete explanation of the study to potential participants and will ensure that all questions are answered prior to decisions about participation. Participation in this clinical trial is completely voluntary and great care will be taken to ensure that individuals do not feel coerced to participate. Subjects will be able to terminate their participation at any time without prejudice. In order to assess the voluntary nature of participation in the study, a decision monitor will speak with all participants prior to beginning the study procedures.

Complete History

A detailed medical history will be obtained from each subject during the first baseline visit to ensure that exclusion from participation is not indicated.

Physical Examination

During baseline and post-vector administration evaluations, physical examinations will be performed. These exams will assess occurrence of systemic adverse events.

Electrocardiogram, Chest X-ray

12-lead electrocardiogram and chest X-ray will be performed at a baseline visit as part of the pre-vector administration evaluation.

Hematology, Chemistries, Urinalysis, Coagulation Panel

Complete blood count, with platelet count, serum chemistries including BUN, creatinine, electrolytes, liver function and coagulation panel tests

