will be obtained. Blood samples will be collected at baseline visit (serving also as a pre-vector administration evaluation) and during post-vector administration evaluations. This testing will help detect toxicity in a number of organ systems. In order to be eligible to participate, all women of childbearing potential must have two negative pregnancy tests within the month prior to study agent administration.

Vital Signs Monitoring

Following vector administration, subjects will be closely observed and vital signs (e.g. blood pressure, pulse, respiration, and temperature) will be monitored. Subjects will be discharged after IOP is confirmed to be less than 30 mm.

AAV Antibody and Antigen-specific Reactivity (ASR) Measurement (For Research Only)

Measurements of neutralizing antibody titers to AAV2 capsid components and ASR assays will be performed at a baseline visit and during post-vector administration evaluations as markers of any systemic immune response to vector administration.

Human ND4 Antibody (For Information Only)

Currently, there is no human ND4 antibody available for detection of transgene expression. In preclinical studies, we used the FLAG tagged ND4 for immunodetection. However, FLAG is not included in the clinical vector. Therefore, on a For Information Only basis, detection of antibodies against the human ND4 transgene will be attempted at a baseline visit and during post-vector administration evaluations as markers of a systemic immune response to the transgene ND4. Serum will be reacted against Western blots of human mitochondrial proteins before and after administration of scAAV2-P1ND4v2. Bands within this size range of P1ND4v2 (approximately 50 kilodaltons) that develop post treatment will be excised and submitted for identification by mass spectroscopy to determine if they are against human ND4.

Peripheral Blood Q-PCR (For Research Only)

To detect vector spread, peripheral blood analysis for vector DNA by Q-PCR will be performed at a baseline visit and following vector administration. If positive (>100 vg) testing will continue until two consecutive samples test negative.

Visual Acuity

Visual acuity is an important outcome variable. Visual acuity is measured before pupil dilation or any other technique that could affect vision.

Refraction is performed prior to formal measurement of ETDRS visual acuity testing at all visits.

Subjective Refraction:

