The paper data forms for the Study are kept in file cabinets in the Biostatistics facility in the Dominion Tower. The building is locked and access is by card key entry. A security guard is present during working hours. The computer files for the study are kept on computers in the same location. These rooms are kept locked when not in use, and the study computer files are password-protected as described in Resources. The data files are backed up daily and are stored at a remote facility. Computer data files used for publication are saved and stored as separate files.

Data Forms

The data forms will be designed to be self-explanatory. Their completion should not require reference to separate information manuals. The data forms contain information to be collected at a given point in time during the study. Information collected at another date is incorporated into a separate form. Data forms are faxed to the

Biostatistics Center for data entry. Forms will be reviewed periodically and revised as dictated by protocol changes.

Data Analysis

The analysis of data will be performed by the Biostatistics Center under the supervision of [name]. He is the principal investigator biostatistics Center for the Phase 1 Safety trial, descriptive statistics with 95% confidence intervals around the success rates and the adverse event rates will be calculated. To reiterate, the results of the ongoing monitoring of each patient's course by the BC and the Data and Safety Monitoring Committee (DSMC) will be evaluated to decide about continuing recruitment in this phase of the trial; statistical considerations will only provide guidelines.

Assessments of change in visual acuity will be calculated from the Baseline 2 measurement to guard against regression to the mean from the screening acuity, Baseline 1.

These patients will also be monitored for ocular and systemic adverse events which will be reviewed by the DSMC on an ongoing basis as deemed necessary by the DSMC and the NEI.

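### Acuity change is counted from Baseline 2, up to a month before injection, while the scheduled Day 0 reading has no stated use; this matters mainly in Group II

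*Combined protocol and SAP*

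**What the plan says.** - **Reference value.** Section 12, Data Analysis: "Assessments of change in visual acuity will be calculated from the Baseline 2 measurement to guard against regression to the mean". The sentence names Baseline 1 as the screening value to be avoided and makes no exception by group.
- **Timing.** Table 6-4 footnote, Section 10: "Baseline visits are no more than 1 month before day 0, date of vector administration". Baseline 2 has no tighter limit of its own.
- **Day 0.** As extracted, the acuity row of Table 6-4 has 15 marks under 15 columns, so Day 0 is marked. The OCT row is blank at Day 0. No analysis that uses a Day 0 acuity is described.
- **Order within a visit.** Section 10, Visual Acuity: "Visual acuity is measured before pupil dilation or any other technique that could affect vision". Step 10 of the injection procedure has the eye dilated before injection unless that has already been done.
- **Selection.** Section 7, Enrollment Procedures: "Eligibility will be assessed at a study team meeting prior to the baseline 2 exam".
- **Safety rules.** Section 3: "Safety will be monitored for loss of 15 letters in Aims 1 and 2", with no reference visit named. For Group III, the note under Table 6-6 defines a vision-related SAE as 15 letters "worse than the worst acuity measured in the uninjected fellow eye at the current or any prior study visit".
- **Natural course.** Section 4 says the disease "usually presents as a loss of central vision that typically progresses over weeks without pain".

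**The concern.** A change score meant to describe what follows an injection should start as close before it as possible. Here it may start up to a month earlier, in a disease that can worsen over weeks. Loss in that gap would look like harm from the vector. Recovery in the gap would look like benefit, and gap loss could hide a later gain. Cohorts have three eyes, so one shifted value is a large share of the evidence.

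The one reason given for Baseline 2 is regression to the mean from Baseline 1. Eligibility is settled before Baseline 2, so neither Baseline 2 nor Day 0 is the qualifying measurement. A pre-injection Day 0 score meets that reason equally well and lies closer to the exposure.

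**Working it through.** The plan states no figure that depends on this choice, so there is nothing to reproduce. The check is a reading by group, then two short calculations.

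**1. Where the gap enters, by group**

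- *Group I* (at least 12 months since onset in one eye, at least 6 in the other): a fall within one month is less likely. The gap matters little, and the benefit of Day 0 is precision.
- *Group II* (under 12 months, both eyes affected): a fall in the gap is plausible. It enters the acuity-change summaries. It enters the 15-letter safety rule only if Section 12 supplies the reference visit that Section 3 omits.
- *Group III* (injected eye still good): the vision-related SAE compares the injected eye with the worst fellow-eye acuity so far. Baseline 2 of the injected eye plays no part, so only the summaries are affected.

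**2. Size in Group II, illustration only**

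The documents give no rate of letter loss, no test-retest SD and no actual Baseline 2-to-Day 0 interval. Assume a gap loss of d = 0, 5, 10 or 15 letters, an SD of a two-visit difference of σ = 5, 8 or 10 letters, and no true change after injection. The chance of a measured loss of 15 letters or more at one follow-up visit is

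P = 1 − Φ((15 − d)/σ).

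| Gap loss d | σ = 5 | σ = 8 | σ = 10 |
|---|---|---|---|
| 0 | 0.1% | 3.0% | 6.7% |
| 5 | 2.3% | 10.6% | 15.9% |
| 10 | 15.9% | 26.6% | 30.9% |
| 15 | 50% | 50% | 50% |

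Measured from Day 0, the first row applies whatever the gap loss. With no gap loss the two references give the same result.

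For a cohort of three with the same gap loss in every eye, the chance of two or more such events is 3P² − 2P³. At d = 10 this is 6.8%, 17.5% and 22.7% from Baseline 2, against less than 0.1%, 0.3% and 1.3% from Day 0.

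These figures lean high for two reasons. First, 10 letters over a full month (4.35 weeks) is 10/4.35 = 2.3 letters a week. At that rate an eye entering at 35 letters reaches zero in 35/2.3 ≈ 15 weeks, so the rate cannot hold across a group that extends to 12 months from onset. Second, an eye below 15 letters at Baseline 2 cannot lose 15, and the formula ignores that floor.

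**3. Precision in stable eyes**

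Let s² be the measurement-error variance of one reading.

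- Change from one baseline: s² + s² = 2s².
- Change from the mean of Baseline 2 and Day 0: s² + s²/2 = 1.5s².
- Reduction: 1 − 1.5/2 = 25%, whatever the value of s.

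**The case against.** Baseline 2 is a prespecified choice with a valid reason. Four further points stand and limit the concern.

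- **Safety and escalation.** A reader might infer that pre-injection loss is charged to the vector in every group's safety rule, and that one such loss would redirect escalation. The documents do not support this. Group III uses the fellow eye. Section 3 names no reference visit for Groups I and II. Section 6 refers to 2 of 3 (or 6) eyes. Section 12 leaves decisions to review of each patient's course by the Biostatistics Center and the monitoring committee, with statistics as guidelines only. The primary hypothesis (no systemic toxicity, no loss to no light perception) depends on no baseline.
- **The gap is a ceiling.** Baseline 1, the eligibility meeting and Baseline 2 come in sequence inside the same month.
- **Day 0 is a partial remedy.** Natural loss after injection counts under either reference.
- **The Day 0 reading is inferred.** Table 6-4 is machine-read and has visible faults: the acuity row is also marked for years 4-10, where Section 10 describes annual contact by mail or telephone. The injection procedure also includes vision checks after the injection on Day 0. The blank OCT cell makes the acuity mark credible, and the dilation rule points to a pre-injection reading, but both need confirming in the original.

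What does not stand is that Baseline 2 protects better against regression to the mean. Nothing in the plan gives it that advantage over a pre-injection Day 0 score.

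**Conclusion.** The point holds in limited form. Acuity change is measured from a visit that may precede injection by up to a month, and a scheduled reading nearer the injection goes unused. The consequence is chiefly in Group II. There, gap change in either direction enters the acuity-change summaries and, if Section 12 governs the 15-letter rule, safety monitoring. In Group III it touches the summaries only. In Group I the case for Day 0 is the 25% reduction in error variance.

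The size in Group II is not known. Under assumed gap losses of 5 to 10 letters, the per-eye chance of a spurious 15-letter loss at one visit is about 2-31% from Baseline 2 and 0.1-7% from Day 0. Those ranges rest entirely on the assumed drift and SD. This is a worthwhile refinement; it does not undermine the trial.

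**What to change.** 1. Confirm in the original Table 6-4 and the Day 0 form that ETDRS acuity is scored on Day 0 before injection. If it is not, only items 3 and 4 apply.
2. Amend the Section 12 sentence so that acuity change is taken from the pre-injection Day 0 score in Groups II and III, and from the mean of Baseline 2 and Day 0 in Group I. Report change from Baseline 2 alongside for every subject, including any already treated.
3. State which reference visit the 15-letter loss in Section 3 uses for Groups I and II, so that Sections 3 and 12 are reconciled.
4. Report the interval from Baseline 2 to Day 0 for each subject and, where Day 0 acuity exists, the acuity change over it for both eyes.

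**Cost.** A short amendment, with no new visit or test if item 1 is confirmed. There are two drawbacks. The groups would have different baseline definitions. The reference would also change part-way through an open-label trial: Section 6 describes escalation to the higher dose as already approved, which suggests earlier cohorts have been treated. Reporting both analyses for everyone lets a reader see whether the switch alters any conclusion.
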